Please note, the primary outcome of interest is CD4 count, which will be collected with a review of participants' medical records following each study visit. Participants' viral load and current antiretroviral therapy regimen will also be extracted from participants' medical records following each study visit. Other measures will be in the REDCap questionnaires that will be administered using iPads.

B. Description of Populations to be Enrolled:

Individual interviews to adapt infographics to the Latino population of Denver, CO
Patient participants for interviews to identify necessary changes to infographics will be adults (≥ 18 years), Hispanic/Latino, English or Spanish-speaking, and living with HIV. If patient participants are pregnant, they may still be included.

RCT - Interventionists

Inclusion criteria for clinicians who will administer the intervention during the RCT will be those who have offered HIV-related care for greater than one year and are not planning to leave the clinic for the next year.

RCT - Patient participants

Inclusion criteria for patient participants for the RCT will be that patients are adult (≥ 18 years), Hispanic/Latino, English or Spanish-speaking, living with HIV with a detectable viral load (>30 or >40 copies/mL depending on the laboratory test) at any point in the past year or be newly diagnosed with HIV, or have an indication of adherence risk as identified by their provider and be planning to receive care at the study site for the next year. If patient participants are pregnant, they may still be included in the study. Participants from the US site are expected to reflect the demographics of Latino patients at the Center for Positive Health (CPH), who are predominantly male (85%) and Mexican (90%). Participants from the DR will reflect the population at CFLR, which is majority female (57%) and Dominican (81%).

Key-stakeholders who participate in in-depth interviews

Key-stakeholders for in-depth interviews to assess implementation factors of incorporating the SMART on FHIR app into electronic health records will be clinicians or other employees at both sites who provide HIV-related education to patients, have been working in HIV care for greater than one year, and interact with the electronic health record at their site on no less than a weekly basis.

Usability testing of Creole version of the mobile app

Table 1. Outcome measures	
Outcome	Measure
Proximal Outcomes	

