D. Description, Risks and Justification of Procedures and Data Collection Tools

Description of data collection tools

D.1. Individual interviews to adapt infographics to the Colorado context.

Participants will initially complete a brief demographic questionnaire. Then, they will complete individual interviews with a study team member. Interviews will be audio recorded and later professionally transcribed.

D.2. RCT

D.2.1. Medical record review

Data will be extracted from medical records after each study visit and will include the primary outcome CD4 count as well as most recent viral load and currently prescribed ART regimen.

D.2.2. Baseline assessments

Baseline assessment will be administered either virtually or in-person at baseline visits and will collect demographics (age, length of time living with HIV, sex, gender, income, level of education among others), assess health literacy levels with two validated assessments, the Short Assessment of Health Literacy - Spanish & English (SAHL S&E)⁶⁵ and the Newest Vital Sign (NVS),⁶⁶ include a measure of acculturation, the Short Acculturation Scale for Hispanics (SASH),⁶⁷ and all other outcome measures not extracted from medical records (Table 1).

D.2.3. Follow up assessments

Follow up assessments will be administered either virtually or in-person at 3-, 6-, and 9-month visits and will include outcome measures (Table 1) and open-ended questions exploring infographic usability, satisfaction with infographic design, and recommendations for improvement. Questions regarding interventionists' communication strategies and intervention delivery will be included to further assess intervention fidelity and enable assessment of providers' communication variability.

D.2.4. Semi-structured in-depth interviews

In depth interviews with patient participants at the CO site will be conducted using a rigorously developed iterative interview guide.⁶³ Interviews at the CO site will include questions and probes to generate an explanatory model of participants' experience living with HIV and communicating about it in a clinical setting,⁶⁸ this data was already collected from participants in the DR and NY in preliminary studies. Questions to obtain feedback on how to adapt infographics and clinical communication will be included for all participants. Interviews will be audio recorded and later transcribed.

D.2.5. Follow up interviews with interventionists

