
The study team will strictly adhere to the procedures detailed in this protocol, including methods to mitigate risks to participants.

Justification of procedures

Because this study involves no more than minimal risks to participants, the above described procedures and data collection techniques are justified as they are all necessary to satisfy the research aims of this study. Additionally, having the option to complete visits virtually or in-person will ensure maximum safety for patients and providers in times of COVID-19 surges.

E. Potential Scientific Problems

As attrition may be a concern in hard to reach populations,⁶⁹ we accounted for 22% attrition in our sample size calculations. To encourage retention, as was successful in the K99 trial in the DR, participants will be reminded of visits via phone calls prior to study visits and incentives appropriate for each site will be provided. Recruitment will be monitored to ensure a sufficient pace of enrollment and timelines will be extended if needed.

Intervention fidelity and contamination are concerns as participants may be scheduled to see the incorrect provider, providers may use infographics with control group participants, or simply may not use infographics. Intervention fidelity will be assessed by providers, patients, and a study team member, and contamination addressed with intent-to-treat analysis.

F. Data Analysis Plan

Sample size calculations

Individual interviews

Up to 15 participants will participate in individual interviews. This sample size was established as 15 participants are likely to be able to identify 90% of usability concerns in informatics-based studies⁷⁰ and as few as 10 are likely to achieve saturation in qualitative studies on specific themes (e.g. the experience of living with HIV) with relatively homogenous samples (e.g. Latino persons of predominantly Mexican origin/descent living in Denver, CO).⁷¹

RCT – Interventionists

Up to 5 interventionists at each site will be purposefully selected to participate. This sample size is based on preliminary feasibility studies.

RCT – patient participants (n=164, 82 at each site, 41 per group)

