To establish sample size for the RCT, we used a longitudinal power analysis approach for testing the “time averaged difference” in two group means for a continuous outcome over time.⁷² This effect size is analogous to Cohen’s D: $(\mu_1 - \mu_2)/\sigma$, where μ_1, μ_2 are the outcome means (averaged over time) in the treatment and control groups, and σ is the standard deviation of the outcome (assumed constant over time and equal for both groups).⁷³ Assuming a slightly less than “medium” effect size of D=0.45,⁷³ 80% power, and two-sided significance level $\alpha=0.05$, the required total sample size ranges from 68-126 depending on the assumed constant pairwise correlation between the 4 repeated measures (which we varied from 0.25 to 0.75) (Table 3). We conservatively assume a correlation of 0.75 which requires a total sample size of 126. To account for 22% attrition, higher than our attrition rate that we experienced in the pilot tests in the Dominican Republic (16%) to account for complications with this hard to reach population of Denver, we increased the sample size to 164 (161.5 rounded up to ensure equal numbers in each group).

Interviews with key stakeholders

Up to 15 interviews with key stakeholders will be conducted at each site (CO and DR). This is based on estimates that 12 interviews per site can lead to saturation of identified themes.^{74,75}

Summary of total sample size per site:

DR total # of participants to be consented to achieve study aims: 100 (maximum recruitment at this site will be 115 to account for failures and withdrawals).

Denver Health total # of participants to be consented to achieve study aims: 121 (maximum recruitment at this site will be 140 to account for failures and withdrawals).

Analytic plan for each study aim

Aim 1: See individual interviews in section C above.

Aim 2: *Conduct a multi-site randomized controlled trial to assess the efficacy of the intervention (infographics administered through a mobile app) as compared to standard care in improving treatment outcomes (CD4 count, viral load, self-efficacy to manage HIV, among others) of PWH and determine how resultant effects vary over time (baseline to 9-months) and between sites (US and CO).*

Table 3. Necessary sample size for testing the time-averaged difference between two groups of equal size				Primary	
		ρ (constant correlation of 4 repeated measures over time)			

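### Chart extraction of CD4 and viral load is tied to study visits with no provision for missed ones, so later outcome values already on file may go uncollected

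*Combined protocol and SAP*

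**What the plan says.** The primary outcome comes from the clinic chart. Section IV.A names CD4 as that outcome, taken from "medical records following each study visit", and gives viral load and ART regimen the same timing. Section IV.D.2.1 repeats it: "Data will be extracted from medical records after each study visit and will include the primary outcome CD4 count". It lists the latest viral load and the current ART regimen with it. The questionnaires are separate: "Follow up assessments will be administered either virtually or in-person at 3-, 6-, and 9-month visits" (IV.D.2.3).

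To enter the trial, patients must "be planning to receive care at the study site for the next year" (IV.B). On losses, IV.E Potential Scientific Problems says "we accounted for 22% attrition in our sample size calculations", without separating loss of questionnaires from loss of chart outcomes. Intent-to-treat is mentioned there only as the answer to contamination.

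The primary analysis (IV.F, Aim 2) is a linear mixed model of CD4 at baseline, 3, 6 and 9 months. A general linear model of the 9-month outcome adjusted for baseline is offered as a simpler alternative. No other approach to missing data is described. No section says what happens to extraction when a study visit does not take place, and none gives a date window for the laboratory values.

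**The concern.** CD4 and viral load are routine clinic results. A patient who skips the 6-month questionnaire, or declines further study visits, may still be in care with a recent result on file. If the research assistant opens the chart only because a study visit has occurred, that result is never taken, and a gap that could have been filled becomes missing data.

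Who would have the gaps matters more than how many there are. Enrolment is aimed partly at people with a detectable viral load or an adherence risk identified by their provider, so missed visits may go with poor adherence and lower CD4. The intervention is meant to improve engagement and the two arms see different providers, so visit-keeping could also differ by arm. A mixed model handles missingness that is explained by the values already observed. It does not remove bias when a missed visit reflects current disengagement that those values do not predict. The 9-month model adjusted for baseline would ordinarily omit anyone without a 9-month value.

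**Working it through.** **1. The plan's own sample size.** Inputs from IV.F and Table 3: D = 0.45, four measures with constant correlation 0.75, "80% power, and two-sided significance level" 0.05.

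Total N = 4 × (1.960 + 0.842)² × [1 + 3 × 0.75] / (4 × 0.45²) = 125.97, so 126 is reproduced. All 18 cells of Table 3 also reproduce. 126 / 0.78 = 161.5, and 4 cells of 41 (two sites, two groups) give 164. The figure is correct as stated.

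**2. What 22% attrition leaves.** 0.22 × 164 = 36.1, leaving about 128. The SD of a four-measure mean, in outcome SD units, is √(3.25 / 4) = 0.901. Power = Φ(0.45 × √(n / 4) / 0.901 − 1.96).

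The documents do not give the share of leavers whose chart holds a usable value, so it is varied as an assumption:

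| Share recovered | n contributing | Power |
|---|---|---|
| 0% | 127.9 | 80.6% |
| 25% | 136.9 | 83.2% |
| 50% | 146.0 | 85.5% |
| 75% | 155.0 | 87.4% |
| 100% | 164 | 89.2% |

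With the pilot's 16% attrition the range is 83.4% (none recovered) to 89.2% (all). These rows count an unrecovered leaver as contributing nothing. The mixed model would use that person's earlier values, so the gains (2.6 points at 25%, 6.8 points at 75%) are upper bounds.

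**3. Precision at 9 months.** Recovering 25% to 75% of 36 adds 9 to 27 values, giving 137 to 155. √(128 / 137) = 0.967 and √(128 / 155) = 0.909, so the standard error of the 9-month contrast falls by about 3% to 9%.

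**4. Bias illustration (all inputs assumed).** Suppose the missing 9-month values lie g SD below what the model predicts. Each arm's mean is then too high by g × its missing fraction. With g = 0.5 and losses of 15% (treatment) and 29% (control), averaging 22%:

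- Treatment: 0.5 × 0.15 = 0.075 SD too high. Control: 0.5 × 0.29 = 0.145 SD too high.
- The 9-month contrast is off by 0.075 − 0.145 = −0.07 SD, which understates benefit. Reversing the losses reverses the sign.
- Time-averaged over four measures by simple averaging: 0.07 / 4 = 0.0175 SD (4% of 0.45) if only 9 months is affected, and 3 × 0.07 / 4 = 0.0525 SD (12% of 0.45) if all three follow-ups are affected equally.

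Milder inputs give less. A 5 to 10 point difference in loss with g of 0.2 to 0.5 gives 0.01 to 0.05 SD at 9 months.

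**5. How strong g = 0.5 is.** At correlation 0.75, the SD of the 9-month value given the three earlier values is √(1 − 3 × 0.75² / 2.5) = √0.325 = 0.57. Given baseline alone it is √(1 − 0.75²) = 0.66. A shortfall of 0.5 SD is therefore 0.76 to 0.88 residual SDs, which is a demanding scenario.

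**The case against.** The strongest reply is that the text gives a time and not a condition. It does not say that a visit must be attended, or that extraction stops when visits stop. The RCT study procedures define visits by interval (baseline, 3, 6 and 9 months), so the instruction could mean each scheduled time point. This stands in part: a reader might infer that the plan orders non-attenders' results to be left out, and it does not. But the protocol also uses the term for an event that happens. US participants come in before their appointment to complete a study visit, and questionnaires are done with a team member at study visits. Taken literally, no one is told to open the chart when nothing took place, and two sites could act differently.

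It can also be said that recovery may be small. Intervention visits are ordinary clinic visits, so someone who misses one may have no new CD4, and planning a year of care is only an intention at entry. Virtual assessments, reminders and incentives already limit missed visits. This stands: the recoverable share is unknown.

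Other stronger readings are tempting but unsupported:

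- That such patients lose their primary outcome. The mixed model retains their earlier CD4 values.
- That seeing a different provider ends extraction. Nothing links extraction to the provider seen.
- That an intent-to-treat promise is broken. The statement concerns contamination only.
- That the trial is underpowered. The 22% allowance exceeds the pilot's 16% and keeps power at about 80.6%.
- That the bias is 16% of the planned effect (0.07 / 0.45). That divides a 9-month bias by a time-averaged effect.

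Consent pages are not in the public file, so permission for record review after a participant stops visits cannot be judged.

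**Conclusion.** The point holds as a gap in the extraction rule, with a better method available at little cost. The protocol times the collection of a chart-based primary outcome to study visits and leaves missed visits uncovered. If applied literally, it creates avoidable gaps at the later time points that may also be selective. The 9-month baseline-adjusted model is the most exposed; the primary mixed model is less so.

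The size is modest and rests on assumptions. Under the fairly severe scenario, bias is 0.07 SD at 9 months and about 0.02 to 0.05 SD on the time-averaged effect; milder inputs give 0.01 to 0.05 SD at 9 months. Extra power is secondary, at most about 3 to 7 points for 25% to 75% recovery. The target of 164 needs no change. The documents support neither a claim that outcomes will certainly be lost nor a figure for how many could be recovered.

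**What to change.** In IV.A and IV.D.2.1, replace the visit-based timing with a rule of this kind:

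*CD4, viral load and ART regimen will be extracted for every randomised participant within a defined window around 3, 6 and 9 months after randomisation, whether or not the study visit took place, unless the participant withdraws permission for record review.*

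State the width of the window. Record withdrawal from visits and questionnaires separately from withdrawal of record access, and continue extraction after the first kind. Include the recovered values, with their actual dates, in the primary mixed model.

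The cost is a protocol wording change, one more option on the withdrawal form, consent wording if the present form does not cover it, and a few extra chart look-ups. The drawback is that some recovered values will fall off schedule, which is why their dates should be kept.

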Permuted block randomization stratified by clinical site will be computer generated a priori and placed in ordered opaque envelopes by a study team member who is not recruiting; thus, group assignments will be blind to the study team.⁶¹ Procedures will then take place as described in Table 2.

Time intervals of study visits (baseline, 3-, 6-, and 9-months) were selected as CD4 count and viral load may change at three months after ART initiation.⁶² Study participants will have visits with interventionists (treatment group) or other providers (control group). Prior to the study, standard education at each site will be evaluated to ensure the only difference between treatment and control groups is the infographic intervention. The intervention will not be administered at 9-month visits to enable assessment of long-term effects. No extra time will be allowed for intervention study visits and participants will be reminded of visits via phone. Half of intervention visits (randomly selected) will be audio recorded and a checklist of intervention components will be independently completed by two study team members, then compared to verify intervention fidelity.

In-depth interviews with key stakeholders

Semi-structured individual interviews will be conducted with up to 15 clinicians at each site who provide patient education to establish preferences and recommendations for integrating the app into each EHR (Aim 3). Interview guides will be rigorously developed⁶³ and questions will be guided with a theoretical model.⁶⁴

Usability testing of Creole version of the mobile application

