Effect Size (Average diff. in 2 group means over time, analogous to Cohen's D: $(\mu_1 - \mu_2)/\sigma$)		0.25	0.50	0.75	
0.20 (Small)		344	491	638	
0.35		113	161	209	
0.40		86	123	160	
0.45		68	97	126	
0.50 (Medium)		55	79	103	
0.80 (Large)		22	31	40	

Note: Calculations with 80% power and $\alpha=0.05$ with 4 repeated measures assuming exchangeable/ constant pairwise correlation " ρ " varied from 0.25 to 0.75.

Analysis: A linear mixed effect model (LMM) will be used to compare the effects of the two groups (treatment vs. standard of care) on the primary longitudinal outcome of CD4 count between baseline and the three follow up visit time points (3-, 6-, and 9-months). Subject-specific random intercepts and slopes will be used to model heterogeneity in the subjects' trajectories. Three primary tests will be considered: 1) testing the time-averaged difference in the outcome between the two treatment groups (main effect for treatment), and 2) test whether change-over-time differs between the two treatment groups (treatment*time interaction), and 3) test whether the treatment effect differs between the two sites (treatment*site interaction and treatment*site*time interaction).

Secondary Analyses: The same analysis plan will be repeated with the remaining longitudinal outcomes Table 2 of the Research Strategy section of this application. Linear mixed effect models (LMM) will be used for continuous outcomes (CD4 count, viral load, knowledge questions, engagement with health care provider scale, satisfaction with care,

self-efficacy, health related quality of life PROMIS-29), logistic generalized linear mixed effect model (GLMM) will be used for the dichotomous adherence score (SMAQ-6), and ordinal GLMM will be used for the health status assessment score while LMM will be used for the additional health status continuous score. Lastly, as a simpler alternative to longitudinal mixed effect models (that use all time points), standard general linear models will be used to model outcomes at 9 months adjusting for baseline, thus testing whether an outcome differs between the two interventions at 9 months.

The System Usability Scale (SUS) that providers complete during the second training session will be scored according to published guidelines.⁷⁶

D.9.4. Aim 3: Assess implementation factors of integrating the SMART on FHIR app into EHRs through in-depth interviews and leverage findings to ensure the app effectively interfaces with EHRs in the CO and the DR.

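### CD4 and viral load are taken from the chart with no draw date, window or single-use rule, so an old result can be entered as a new 3-, 6- or 9-month measurement

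*Combined protocol and SAP*

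**What the plan says.** Section IV.A states that "the primary outcome of interest is CD4 count, which will be collected with a review of participants' medical records following each study visit". Section D.2.1 repeats this: extraction follows each study visit and "will include the primary outcome CD4 count as well as most recent viral load". The words *most recent* qualify viral load only.

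Table 2 (Section C, RCT study procedures) lists randomisation, assessments, standard care, exposure to the intervention and interviews. It lists no blood draw. Virtual visits are allowed throughout: "Baseline assessment will be administered either virtually or in-person at baseline visits" (D.2.2) and "Follow up assessments will be administered either virtually or in-person at 3-, 6-, and 9-month visits" (D.2.3). Section C also foresees telehealth clinic visits in the treatment group.

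The visit intervals "were selected as CD4 count and viral load may change at three months after ART initiation" (Section C), so the design expects CD4 to be able to move from one visit to the next. The primary analysis (Section F, Aim 2) compares the groups on the "primary longitudinal outcome of CD4 count between baseline and the three follow up visit time points (3-, 6-, and 9-months"). It tests the time-averaged difference, treatment\*time, and the treatment\*site terms.

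No section gives a draw date, a window around a visit, a bar on using one result at two visits, or an instruction to record a missing value when there is no new result.

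**The concern.** The person abstracting the chart after a month-3 visit with no new laboratory result has no CD4 instruction beyond recording a value. For viral load, the instruction is to take the latest one. If that result predates the previous visit, last observation carried forward enters the data as if it were a measurement. Because the draw date is not kept, the analyst cannot separate fresh values from stale ones afterwards.

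A follow-up value copied from baseline cannot contain any effect of the randomised intervention. All the primary tests are exposed. The average difference can shrink, the shape over time changes, and a difference between clinics in laboratory frequency can look like a difference in treatment effect between sites.

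**Working it through.** **1. The plan's own figure.** Inputs from Section F: D = 0.45, correlation 0.75, m = 4 measures, 80% power, two-sided 0.05. Total N = 4(1.960 + 0.842)² × [1 + (m − 1) × 0.75] / (m × D²) = 7.849 × 3.25 / 0.2025 = 125.97, so 126. Then 126 / 0.78 = 161.5, raised to 164. The plan's figures reproduce, and nothing below changes them.

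That formula applies D at all four measures, baseline included. Read literally, reuse would only raise the correlation, and N would become 130 at 20% reuse and 134 at 40%. The dilution below arises because a baseline value in a randomised trial carries no treatment effect.

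**2. Dilution with equal reuse in both arms.** Assumption, not in the documents: each follow-up value is, independently with probability p, a copy of the previous recorded value. If E_k is the true effect at follow-up k and R_k the recorded one, then R_k = (1 − p)E_k + pR_(k−1), with R_0 = 0.

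| True effect (months 3, 6, 9) | p | Recorded | Share of follow-up average kept |
|---|---|---|---|
| Constant: 1, 1, 1 | 25% | 0.750, 0.938, 0.984 | 2.672 / 3 = 89% |
| Constant: 1, 1, 1 | 50% | 0.500, 0.750, 0.875 | 2.125 / 3 = 71% |
| Linear: 1/3, 2/3, 1 | 25% | 0.250, 0.563, 0.891 | 1.703 / 2 = 85% |
| Linear: 1/3, 2/3, 1 | 50% | 0.167, 0.417, 0.708 | 1.292 / 2 = 65% |

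In the constant rows, a flat effect is recorded as one that grows. That is a distortion of treatment\*time.

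**3. Reuse that differs by arm.** Take no true effect and a rise in both arms of 0.1, 0.2 and 0.3 SD at months 3, 6 and 9.
- At 20% reuse (treatment), the recorded rises are 0.080, 0.176 and 0.275, mean 0.177.
- At 40% reuse (control), they are 0.060, 0.144 and 0.238, mean 0.147.
- The false difference is +0.03 SD. Swapping the rates gives −0.03 SD.

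**4. Reuse that differs by site.** With the same constant effect of 0.45 SD at both sites, 25% reuse at one and 50% at the other, the recorded averages are 0.891 × 0.45 = 0.401 and 0.708 × 0.45 = 0.319. The apparent site difference is 0.08 SD.

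**5. Power, for illustration only.** The answer depends on the model and on the assumed effect.
- Unadjusted follow-up mean, D = 0.45, N = 126: 79% with no reuse, 71% at 20% reuse, 57% at 40%.
- Baseline-adjusted follow-up mean, 64 per arm, 0.45 SD: 99.6% with no reuse, about 99% at 25% and 95% at 50%.
- The same baseline-adjusted model at 0.30 SD: 90% with no reuse, 83% at 25% and 71% at 50%. If the values without a draw are instead set to missing (at random, constant-effect mixed model), power is about 86% and 77%. At 25%, the rule therefore recovers about 3 of the 7 points lost, and at 50% about 6 of 19. The rest is lost because no draw exists.

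None of these is the planned random-slope model with baseline as an outcome.

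**The case against.** The strongest reply is that the protocol contains no carry-forward rule for CD4. The phrase *most recent* belongs to viral load. Leaving CD4 missing when there is no new result fits the text equally well, and the mixed model would accommodate it. The three-month spacing suggests that a fresh value was expected, and recruitment is built around regularly scheduled appointments. Virtual visits are an option whose frequency is not given, and a laboratory draw on another day is not excluded. All of this stands. A reader might infer that the plan prescribes wrong CD4 values at months 3, 6 and 9. The documents do not support that: they leave the matter open.

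A reader might also infer that baseline is contaminated because it is extracted after the visit at which treated participants are first exposed. That confuses the time of abstraction with the time of the draw. A sample taken on or before the visit day is unaffected by when it is copied from the chart.

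The reply does not remove the gap. Nothing tells the abstractor which reading to follow, nothing in the extracted data would show which was followed, and for viral load the reuse rule is explicit.

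**Conclusion.** The concern holds as a gap in the definition of the primary outcome and as a stated reuse rule for viral load. It should be closed before analysis.

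Under equal, independent reuse in both arms at an assumed 25% to 50%, the follow-up average loses 11% to 29% of a constant effect and 15% to 35% of a linearly growing one. The documents give no reuse rate, laboratory frequency or share of virtual visits, so the actual size cannot be determined from them.

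It would be tempting to say that the effect is simply pulled toward zero. That requires similar reuse in both arms. Treated participants see selected interventionists and controls see other providers, so testing frequency may differ, and the bias can then go either way. The power figures should not be read as a forecast. They rest on an assumed p, and part of the loss would remain under any analysis rule.

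**What to change.** Add to D.2.1 and to the Aim 2 analysis plan:

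- Extract the draw date with every CD4 and viral load result.
- Take baseline as the last draw on or before randomisation, within a stated look-back.
- Assign a result to a follow-up visit only if it was drawn within a prespecified window, whose width the sponsor chooses, and never use one draw for two visits.
- If there is no eligible draw, set the value to missing in the mixed model, and state that this is valid under missing at random.
- Report the share of visits with an in-window result by arm and by site.
- Run a sensitivity model using actual draw time instead of nominal month.

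The cost is one extra chart field, a paragraph of rules, and some visits that become missing. No added blood draws and no change to the planned 164 participants are needed. If the charts hold the draw dates, the rule can also be applied retrospectively before analysis.
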